## **7.6 Orelvo/Placebo Dose Modification**

Dose modifications for background therapy (MMF and corticosteroids) are detailed in Section [7.2, Drug Dosage and Administration](#).

### **7.6.1 Deterioration in Renal Function**

Serum creatinine and eGFR utilizing the CKD-EPI formula will be used for the assessment of renal function at every visit (Visits 1-15 and unscheduled visit(s)). Subjects will have a minimum of 2 eGFR measurements conducted prior to dosing at Visit 2. The lowest of the pre-dose eGFR assessments will be used as the marker of baseline renal function.

It is recognized that eGFR may be unreliable at higher values ( $>100$  mL/min/1.73 m^2). Lupus nephritis subjects with nephrotic range proteinuria frequently have wide fluctuations in serum creatinine (and therefore eGFR) which are not representative of true renal dysfunction. Chronic kidney disease is defined as eGFR  $<60$  mL/min/1.73 m^2 for  $\geq 3$  months [20], with or without kidney damage.

#### **7.6.1.1 Decrease in eGFR $>30\%$ and eGFR $<60$ mL/min/1.73 m^2**

During the treatment period, any subject experiencing a  $>30\%$  decrease in eGFR from baseline to  $<60$  mL/min/1.73 m^2, will have study treatment interrupted until a repeat test can be performed (unscheduled visit to be completed). If the decrease is confirmed and not due to potential contributing factors (e.g., high baseline eGFR, the addition or modification of non-steroidal anti-inflammatory drugs (NSAIDs), angiotensin converting enzyme (ACE) inhibitors, angiotensin II receptor blockers (ARBs), a concurrent state of dehydration, overdosing with study treatment, lupus renal flare, etc.), the case should be discussed with the

Medical Monitor, the study treatment should be withheld, and eGFR retested within 48 hours. If the eGFR decrease is not confirmed, the study treatment can be restarted at 2 capsules BID and increased as tolerated with discussion with the Medical Monitor.

#### **7.6.1.2 Decrease in eGFR $\leq$ 30% and eGFR $<$ 60 mL/min/1.73 m^2**

During the treatment period, any subject having a  $\leq$ 30% reduction in eGFR to  $<$ 60 mL/min/1.73 m^2, should have the influence of potential contributing factors (as described in Section 7.6.1.1, **Decrease in eGFR  $>$ 30% and eGFR  $<$ 60 mL/min/1.73 m^2**) ruled out and appropriate corrective action taken. Any subject having a  $>$ 20- $\leq$ 30% reduction compared to baseline in eGFR to  $<$ 60 mL/min/1.73 m^2 will have a confirmation measurement done within approximately 2 weeks (at a planned study visit, if any, or an unscheduled visit is to be completed). The subjects will be managed in the most medically appropriate manner in consultation with the Medical Monitor. The management of the decrease in eGFR may include reduction of dose or temporary interruption.

#### **7.6.1.3 Recovery of eGFR**

Subjects experiencing a decrease in eGFR with resultant decrease in dose should be reassessed for recovery of renal function. If the repeated eGFR is  $>$ 80% of baseline, the dose should be increased by 1 capsule BID and eGFR assessed within 2 weeks.

### **7.7 Procedures for Overdose**

Based on clinical experience with Orelvo, symptomatic treatment of AEs or overdoses is indicated. Treatment for renal dysfunction, hypertension, and infection may include dose reduction or dose discontinuation. Magnesium supplementation may be required for hypomagnesemia. Treatment for GI complaints and biochemical/hematological abnormalities, and all other expected AEs, should be based on symptoms, with care taken to rule out other causes.

### **7.8 Prohibited Therapy and Concomitant Treatment**

Any concomitant treatment given for any reason during the course of the study must be recorded in the eCRF and in the subject's source documents, including dosage, start and stop dates, and reason for use.

Any class of medications not mentioned below and with the potential to interfere with evaluation of the study treatment must be discussed and documented with the Medical Monitor.

### 7.8.1 Prohibited Medications

The following medications cannot be taking during the study:

- IV corticosteroids within 2 weeks prior to screening (Visit 1) unless approved by the Medical Monitor
- Enteric-coated oral corticosteroids during the study are not allowed. No other use of non-enteric coated oral corticosteroids, other than administration required as per protocol, is allowed
- IV immunoglobulin treatment within 2 weeks prior to screening (Visit 1)
- Cyclophosphamide within 4 weeks prior to screening (Visit 1)
- Cholestyramine or other drugs that may interfere with enterohepatic recirculation of MMF within 4 weeks prior to screening (Visit 1)
- Initiation of new treatment or change in dosage of ARBs and/or ACE inhibitors within 4 weeks prior to randomization (Visit 2)
- CNIs (e.g., cyclosporine and tacrolimus) within 1 month of screening (Visit 1)
- Immunosuppression biologic agents (e.g., abatacept, belimumab, infliximab, adalimumab, etanercept, or rituximab) within 3 months prior to screening (Visit 1)
- Vaccines using live organisms, viral or bacterial
- MMF dose other than 2 g/day without prior discussion with the Medical Monitor
- Concomitant therapy with other immunosuppressants after randomization, other than MMF administered per protocol
- Subjects are allowed to be on AZA or mycophenolate sodium during screening but must switch to MMF at randomization
- Current or planned use of ketoconazole or rifampin
- Concomitant use of other CYP3A4/5 inhibitors and inducers should be discussed with the Medical Monitor

[Appendix 8](#) contains a summary of additional treatment and food restrictions.

### 7.8.2 Allowed Concomitant Medications

These medications are permitted during the study:

- Topical steroids (e.g., nose, scalp, skin, inhaled)
- Antimalarials should be prescribed when clinically indicated
- Herbal supplements can be used with caution and depending on active ingredients

Treatments which may be used as medically indicated, according to the judgment of the Investigator can be found in [Appendix 7](#). Treatments not included in this list may be acceptable in the study; such treatments should be verified with the Medical Monitor prior to use. A summary of treatment and food restrictions can be found in [Appendix 8](#).

### 7.9 Increased Blood Pressure

For all subjects, the target systolic pressure is  $\leq 130$  mmHg and the target diastolic pressure is  $\leq 80$  mmHg. Investigators should use all means possible permitted in the protocol to maintain the BP within these limits. If no further adjustment of antihypertensive therapy is possible, the subject should be discussed with the Medical Monitor.

If on any study day, systolic BP is  $>165$  mmHg or diastolic BP is  $>105$  mmHg and is associated with symptoms of hypertension (i.e., persistent headache, altered mental status, shortness of breath, chest pain consistent with angina pectoris, symptoms of heart failure, evidence of renal insufficiency of new onset, evidence of hypertensive retinal injury [hemorrhages, papilledema]), study treatment should be held, the Medical Monitor contacted, and the subject treated as per Investigator local practices and best judgment. The subject will continue with all study visits per the [Schedule of Events](#). Study treatment must not be reintroduced without prior discussion with the Medical Monitor.

## **8. RISKS/PRECAUTIONS**

No evidence available at the time of the completion of this study protocol indicated that special warnings or precautions are required, other than those noted in the IB.

If additional special warnings or precautions become apparent before study completion, Aurinia will notify the Investigator at each site.

## 9. STUDY PROCEDURES

### 9.1 Description of Study Assessments

#### 9.1.1 Laboratory Assessments

Analysis of all samples for hematology, chemistry, hepatic function, lipid profiles, and urinalysis will be performed at a central laboratory using standard validated methods (see the laboratory manual). All study data analyses involving laboratory values will be based on results from the central laboratory.

The UPCr will be calculated both from the first morning void and from standard urinalysis results. If the first morning void is for some reason not available, then standard urinalysis from a 24-hour urine collection may be substituted as an exception but only after agreement is reached with the Medical Monitor.

Blood and urine samples for the following efficacy and safety assessments (See [Table 2](#)) will be drawn in accordance with the [Schedule of Events](#).

**Table 2 Review of Laboratory Assessments**

Test Type	Test Parameters	Collection at Visits
Hematology	Complete blood count (CBC)	All except Day 2
	Hematocrit	
	Hemoglobin	
	Mean corpuscular hemoglobin (MCH)	
	Mean corpuscular hemoglobin concentration (MCHC)	
	Mean corpuscular volume (MCV)	
	Platelet count	
	Red blood cells (RBC)	
	Red blood cell morphology	
	White blood cells (WBC)	
	Differential (absolute and %)	All except Day 2
	Bands	
	Basophils	
	Eosinophils	
	Lymphocytes	
	Monocytes	
	Neutrophils	
	Erythrocyte sedimentation rate	Day 1, Week 24, and Week 52

Table 2 Review of Laboratory Assessments (Cont'd)

Test Type	Test Parameters	Collection at Visits
Coagulation	Coagulation Activated partial thromboplastin time (aPTT) Prothrombin time (PT) Partial thromboplastin time (PTT)	Screening
Blood Chemistry	Alanine aminotransferase (ALT) Albumin Alkaline phosphatase (ALP) Aspartate aminotransferase (AST) Bicarbonate Bilirubin (direct and total) Blood urea nitrogen (BUN) Calcium Chloride Cholesterol (total, HDL, and LDL) Creatine kinase Creatinine Gamma-glutamyl transferase (GGT) Glucose Glycosolated hemoglobin (HbA1c) Lactic dehydrogenase (LDH) Magnesium Phosphorous, inorganic Potassium Protein, total Sodium Triglycerides c-Reactive Protein	All except Day 2          Day 1, Week 24, and Week 52 Day 1, Week 24, and Week 52      Day 1, Week 24, and Week 52    Day 1, Week 24, and Week 52    Screening, Week 24, and Week 52
Urinalysis	Complete urinalysis (to include urine protein, creatinine, blood, urine microscopy). First morning void will be performed to analyze urine protein/creatinine ratio. A 24-hour UPCR may be substituted for FMV at entry (or endpoint) if required.	All except Day 2
Pregnancy Test	A serum pregnancy test will be performed for females of childbearing potential. Urine pregnancy tests will be done using a dipstick.	Screening and Weeks 24 and 52 (Serum) All other applicable visits (Urine)

Table 2 Review of Laboratory Assessments (Cont'd)

Test Type	Test Parameters	Collection at Visits
Lupus Markers	Anti-double-stranded DNA (anti-dsDNA) antibodies Anti-nuclear antibodies (ANA) Serum Complement 3 Complement 4 Antiphospholipid antibodies Anticardiolipin antibodies Lupus anticoagulant test	Screening, Week 24, and Week 52
Serology	Cytomegalovirus Hepatitis A, B, and C Hepatitis B surface antigen (HBsAg)	Screening
Special Tests	Estimated glomerular filtration rate (eGFR)	All except Day 2

Notes: FMV = first morning void; HDL = High-density lipoprotein; LDL = Low-density lipoprotein; UPCR = urine protein creatinine ratio.  
Baseline renal function will be the minimum value of any and all eGFR values taken during the screening period and at baseline prior to administration of drug (a minimum of the screen and baseline (pre-dose) values. The central lab will need to report a baseline value for the analysis.

The total amount of blood that will be collected during the study from an individual subject is approximately 300 mL over 56 weeks.

For details on whether laboratory abnormalities should be reported as AEs and on the follow-up required in such cases, see Section 10.2.5, [Clinical Laboratory Evaluations](#).

#### 9.1.1.1 Evaluation of Biomarkers

Samples for biomarker assessments will be obtained in blood / urine and stored (frozen) for future analysis for subjects who consent to have their leftover samples retained.

#### 9.1.2 Physical Examinations

Physical examinations will be performed in accordance with the [Schedule of Events](#).

The physical examination will include a review of SLE-related manifestations which will also be recorded. A complete physical examination will be conducted at screening and an abbreviated physical will be performed at all other visits as per the [Schedule of Events](#). The abbreviated examination will consist of checking the normality or abnormality of the following body systems: general appearance, cardiovascular system, and pulmonary system. Any abnormalities will be recorded in the eCRF and reported as an AE. Because the investigational

medication is an immunosuppressant, physical examination will include clinical examination for tumors.

Subject weight will also be recorded at each physical examination; however, height will only be recorded at the screening (Visit 1).

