#### **10.2.4 Symptoms of the Disease Under Study**

Symptoms of the disease under study will not be classed as AEs as long as they are within the normal day-to-day fluctuation of the disease. An explanation of these circumstances must be written in the source documents.

Worsening of the symptoms however, will be recorded as an AE, and clearly marked as worsening or by the subject's worst observed intensity.

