In order to avoid bias in eliciting AEs, subjects should be asked a non-leading question, such as "How are you feeling?" It is also important to question the subject in a non-leading way about changes in their health or concomitant medication usage since their last visit. This information should be collected prior to completion of assessments at all study visits. In addition, any symptoms/conditions reported during assessments and deemed to be clinically significant by the Investigator will be considered AEs.

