### 6.13.1 Adverse Events

A treatment emergent adverse event (TEAE) is defined as:

- Any AE that has an onset on or after the first dose of study drug up to last dose + 30 days. For subjects consenting to the AURORA 2 continuation study there will be an additional constraint to the TEAE definition: events must have an onset date prior to the first dose of AURORA 2 study drug.

A treatment-related TEAE is defined as a TEAE that is assessed by the Investigator or Sponsor as being related to study drug. If a TEAE has a missing relationship to study drug it is assumed to be related to the study drug for analysis purposes.

A disease-related TEAE is defined as a TEAE that is assessed by the Investigator or Sponsor as being related to the disease under study. If a TEAE has a missing relationship to the disease under study it is assumed to be related to the disease under study for analysis purposes.

Missing severity assessments will be summarised as severe.

The following tables will be presented for AEs:

- Summary table of overall incidence, the number of events, risk difference and 95% CI (voclosporin-placebo) including the following top line summaries:
  - Any AE
  - Any TEAE
  - Any Treatment-Related TEAE
  - Any Serious TEAE
  - Any Treatment-Related Serious TEAE
  - Any TEAE Leading to Voclosporin/Placebo Discontinuation
  - Any TEAE Leading to Death
  - Treatment-Related TEAE Leading to Death
  - Disease-Related TEAE
  - Disease-Related Serious TEAE

Detailed list of AE tables is given at the end of this SAP.

In counting the number of AEs reported, a continuous event (i.e., reported more than once and which did not cease), will be counted only once for a subject; a non-continuous AE reported several times by the same subject will be counted as multiple events.

Additional tables for serious TEAEs will be provided for each of the four regions: North America, Latin America, Europe/South Africa and Asia Pacific. Similar tables will also be provided for serious TEAEs occurring between day 1 and day 84 (Up to week 12), day 85 to day 168 (Week 12 to 24) and greater than day 168 (after week 24).

All AEs will be listed and a glossary of unique verbatim terms with coding information will be provided.

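### Protocol 9.1.2 makes any physical-examination abnormality an AE, which contradicts 10.2.4 and lets pre-existing findings be counted differently from site to site

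*Protocol*

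**What the plan says.** Protocol 9.1.2 provides for a complete examination at screening and an abbreviated one at the other examination visits, which the Schedule of Events places at Day 1, Week 24 and Week 52. The abbreviated examination covers "general appearance, cardiovascular system, and pulmonary system". The next sentence is the rule at issue: "Any abnormalities will be recorded in the eCRF and reported as an AE". The same section adds: "The physical examination will include a review of SLE-related manifestations which will also be recorded".

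Other sections set other thresholds:

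- Protocol 10.2.4: "Symptoms of the disease under study will not be classed as AEs as long as they are within the normal day-to-day fluctuation" of the disease. Then: "Worsening of the symptoms however, will be recorded as an AE".
- Protocol 10.3.1: "any symptoms/conditions reported during assessments and deemed to be clinically significant by the Investigator will be considered AEs".
- Protocol 10.2.5: a laboratory change can be an AE if it is clinically relevant, shifts from normal to pathological, or worsens an already pathological value.
- Protocol 9.1.4: ECG abnormalities are recorded in the eCRF; automatic AE reporting is not required.
- SAP 6.13.5: examination results are listed with a yes/no flag for clinically significant abnormality.

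SAP 6.13.1 defines a TEAE as "Any AE that has an onset on or after the first dose of study drug up to last dose + 30 days". Its overall summary gives a risk difference with 95% CI and includes both an Any AE row and an Any TEAE row.

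**The concern.** Subjects enter with active lupus nephritis, and many may carry long-standing findings. Under 9.1.2 such a finding is an AE because it is abnormal. Under 10.2.4 a disease symptom is an AE only once it moves beyond its usual fluctuation. Nothing says which section governs a lupus finding seen at an examination, so sites may differ in what they report.

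At stake is the readability of the safety tables for the affected terms. Findings that have nothing to do with study drug would be counted in both arms, and true new events would have to be seen against that background. In a safety comparison, added noise makes a real difference harder to see.

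**Working it through.** The plan states no figure on this point, so there is nothing to reproduce. The check has three steps.

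**1. The rules side by side**

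| Source | What makes a finding an AE |
|---|---|
| Protocol 9.1.2 | Being abnormal |
| Protocol 10.2.4 | Worsening beyond usual disease fluctuation |
| Protocol 10.2.5 (laboratory) | Clinical relevance, shift from normal, or worsening |
| Protocol 10.3.1 | Clinical significance, as an added route |
| SAP 6.13.5 | No AE rule, but expects a significance flag |

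Section 9.1.2 is the only one without a test of change or importance. It contradicts 10.2.4 for disease findings. With the other three it is out of line but not in direct contradiction.

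**2. Where a pre-existing finding would be counted**

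- *Any AE row (SAP 6.13.1).* This row has no onset filter, and AE reporting starts at consent (Protocol 10.3.1). A finding reported under 9.1.2 counts here even with a correct onset date.
- *TEAE tables, onset dated Day 1.* Protocol 9.2.2 puts Day 1 procedures before the first dose, on the same calendar date. Protocol 13.9 defines TEAEs by date, so such a finding qualifies. Footnote 13 of the Protocol Schedule of Events excludes events before the first dose, so it does not. SAP 6.13.1 does not say whether time of day is used.
- *TEAE tables, onset dated from the Week 24 or Week 52 examination.* A chronic finding dated this way qualifies.
- *TEAE tables, onset missing.* SAP 6.2.6 sets a missing start of an ongoing event to the first-dose date. SAP 6.2.5 switches this off when other eCRF data contradict it, so the route is open only when nothing else in the eCRF dates the finding.

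**3. What the extra counts do**

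Inputs: 162 per arm (Protocol 13.2). Assumed, because the documents give neither: new-event risks of 20% and 10% in subjects without the finding, and a share q of subjects in each arm who already have it. Also assumed at first: subjects with the finding add no further event under that term.

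- Pre-existing findings counted: risk = q + (1 − q)p
- Pre-existing findings not counted: risk = (1 − q)p
- SE of the difference = √[(r₁(1 − r₁) + r₂(1 − r₂))/162]

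| q | Counted: risks | Difference | Ratio | SE | Not counted: risks | Difference | Ratio | SE |
|---|---|---|---|---|---|---|---|---|
| 5% | 24.0% v 14.5% | 9.5 | 1.66 | 4.3 | 19.0% v 9.5% | 9.5 | 2.00 | 3.8 |
| 20% | 36% v 28% | 8.0 | 1.29 | 5.2 | 16% v 8% | 8.0 | 2.00 | 3.6 |
| 40% | 52% v 46% | 6.0 | 1.13 | 5.5 | 12% v 6% | 6.0 | 2.00 | 3.2 |

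(Differences and SEs in percentage points.)

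At q = 20%, counted: √[(0.36 × 0.64 + 0.28 × 0.72)/162] = √(0.432/162) = 0.052. Not counted: √[(0.16 × 0.84 + 0.08 × 0.92)/162] = √(0.208/162) = 0.036. The 95% half-widths are 1.96 × 5.16 = 10.1 points and 1.96 × 3.58 = 7.0 points.

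The added q is the same in both arms and cancels from the difference. The ratio moves towards 1 and the interval widens.

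If subjects with the finding can also worsen, with risk w, and worsening is counted, the second formula becomes (1 − q)p + qw. The point difference then departs from the counted version by q times the between-arm difference in w. The documents give no value for w.

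For the Any TEAE row, w is the chance of some other event. Protocol 1.2.4.2 reports over 90% of Phase 2 subjects with at least one AE, so there is little room. With assumed risks of 93% v 90% and q = 20%, the row reads 0.93 + 0.07 × 0.2 = 94.4% v 0.90 + 0.10 × 0.2 = 92.0%, a difference of 2.4 points instead of 3.0.

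**The case against.** The best defence has four parts.

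First, TEAE status depends on onset, not on when a finding was seen. Protocol 10.3.1 requires an onset date for each AE, and SAP 6.13.1 counts a continuous event once per subject. This stands. A reader might infer from 9.1.2 that pre-existing lupus findings automatically become TEAEs; the documents do not support that. Entry needs one of the dating routes above.

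Second, the sentence in 9.1.2 follows the abbreviated examination, which names three items and neither skin nor joints, while lupus manifestations are only to be recorded. This is a fair reading and narrows the scope. It still covers Day 1, where the dating conflict arises.

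Third, 10.3.1 presents clinical significance as an addition to other routes, so it does not exclude anything, and 10.2.4 speaks of symptoms while examinations mostly yield signs. Both points stand. They reduce the matter to one contradiction (with 10.2.4) and a difference of threshold elsewhere. A site could treat 10.2.4 as the specific rule that overrides 9.1.2, but no text says so.

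Fourth, SLE and medical history are already taken at screening and tabulated (SAP 6.7). That helps to date findings correctly, but does not stop 9.1.2 from requiring an AE report as well.

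A reader might also infer that counting these findings shrinks each term's risk difference by the factor (1 − q). The table shows otherwise: the 8-point and 6-point differences appear under both rules. They fall below 10 because fewer subjects are at risk of a first occurrence, and rewording 9.1.2 does not change that.

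**Conclusion.** The contradiction between 9.1.2 and 10.2.4 is real and should be reconciled; it is a minor point. It allows uneven AE capture between sites, puts pre-existing findings in the Any AE row, and leaves open whether a finding from the Day 1 pre-dose examination is a TEAE.

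For affected terms the consequence is non-differential counts: ratios nearer 1 and wider intervals for the risk difference, with no general shrinkage of the difference itself. The size cannot be stated, because neither the share of affected subjects nor their risk of worsening is given. The figures above are illustrations that assume equal shares in the two arms. The primary efficacy analysis and the sample size are untouched, and 9.1.2 alone does not affect serious TEAEs.

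**What to change.** Replace the sentence in Protocol 9.1.2 with wording such as: abnormalities are recorded on the examination form; those present before informed consent are entered in medical history; findings that are new or worse since consent are reported as AEs in line with 10.2.4 and 10.3.1. The cut-off has to be consent, not first dose, because 10.3.1 starts AE reporting at consent.

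In Protocol 13.9 and SAP 6.13.1, add that findings from the Day 1 pre-dose examination are not TEAEs, so that both agree with footnote 13 of the Protocol Schedule of Events.

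The cost is one protocol sentence, one clarification in each document and brief site guidance on dating onset. The downside is slightly fewer AE records; every abnormality remains on the examination form.
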